- Hemoglobin > 11.0 g/dL or 50% improvement over baseline without transfusions or erythropoietin support.

Progressive Disease (PD) requires at least one of the following:

1. Appearance of any new lesions such as enlarged lymph nodes (> 1.5 cm), splenomegaly, hepatomegaly or other organ infiltrates.

2. $\geq 50\%$ increase in the sum of the products of diameters of multiple nodes
3. $\geq 50\%$ in the greatest determined diameter of any previous site. A lymph node of 1-1.5 cm must increase by $\geq 50\%$ to a size greater than 1.5 cm in the longest axis. A lymph node of more than 1.5 cm must increase to more than 2.0 cm in the longest axis.
4. $\geq 50\%$ increase in the size of the liver and/or spleen or the de novo appearance of hepatomegaly or splenomegaly.
5. $\geq 50\%$ increase in the absolute number of blood lymphocytes with at least 5,000 B-lymphocytes per μL .
6. Transformation to a more aggressive histology (e.g., Richter's syndrome or PLL with $> 55\%$ prolymphocytes).
7. Occurrence of cytopenia (neutropenia, anemia or thrombocytopenia) attributable to CLL.
 - The progression of any cytopenia (unrelated to autoimmune cytopenia), as documented by a decrease of Hb levels by more than 2 g/dL or to less than 10 g/dL, or by a decrease of platelet counts by more than 50% or to less than 100,000/ μL , defines disease progression, if the marrow biopsy demonstrates an infiltrate of clonal CLL cells.

Subjects who have not achieved a CR or a PR, or who have not exhibited PD will be considered to have Stable Disease (SD).

A summary of the criteria described above is included in [Table 11](#).

Table 11. IWCLL Updated NCI-WG Criteria for Tumor Response (2008)

Criteria	Complete Remission (CR)	Partial Remission (PR)	Progressive Disease (PD)	Stable Disease (SD)
Lymphadenopathy	None above 1.5 cm	≥ 50% reduction	≥ 50% increase	Change of -49% to +49%
Hepatomegaly and/or Splenomegaly	Absent	≥ 50% reduction	≥ 50% increase or new hepatomegaly and/or splenomegaly	Change of -49% to +49%
Constitutional Symptoms	Absent	Present	Present	Present
Polymorphonuclear Leukocytes	≥ 1500/μL	≥ 1500/μL or > 50% improvement over baseline without G-CSF support	Not specified	Not specified
Circulating clonal B-lymphocytes	None	≥ 50% reduction from baseline	≥ 50% increase over baseline	Change of -49% to +49%
Platelets	> 100,000/μL	> 100,000/μL or ≥ 50% improvement from baseline	Decrease of ≥ 50% from baseline secondary to CLL	Change of -49% to +49%

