6.1 Definitions

6.1.1 Adverse Event

An adverse event (AE) is defined as any untoward medical occurrence in a patient or clinical investigation subject administered a pharmaceutical product and which does not necessarily have a causal relationship with this treatment. An adverse event can therefore be any unfavorable and unintended sign (including an abnormal laboratory finding), symptom, or disease temporally associated with the use of a medicinal (investigational) product, whether or not the event is considered causally related to the use of the product.

Such an event can result from use of the drug as stipulated in the protocol or labeling, as well as from accidental or intentional overdose, drug abuse, or drug withdrawal. Any worsening of a pre-existing condition or illness is considered an adverse event.

Laboratory abnormalities and changes in vital signs are considered to be adverse events only if they result in discontinuation from the study, necessitate therapeutic medical intervention, meets protocol specific criteria (see Section 6.7 regarding toxicity management) and/or if the investigator considers them to be adverse events.

An elective surgery/procedure scheduled to occur during a study will not be considered an adverse event if the surgery/procedure is being performed for a preexisting condition and the surgery/procedure has been pre planned prior to study entry. However, if the pre-existing condition deteriorates unexpectedly during the study (e.g., surgery performed

earlier than planned), then the deterioration of the condition for which the elective surgery/procedure is being done will be considered an adverse event.

Hospitalization for the purpose of TLS prophylaxis (e.g., for I.V. hydration) will not be captured as a serious adverse event (SAE), unless there is an additional reason for hospitalization or an additional criterion for seriousness other than hospitalization.

A treatment-emergent adverse event is defined as any adverse event with onset or worsening reported by a subject from the time that the first dose of study drug is administered until 30 days have elapsed following discontinuation of study drug administration.

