All analyses involving AEs were treatment-emergent adverse events (TEAE) only, unless otherwise specified. TEAE were defined as any event with onset after the first dose of navitoclax and no more than 30 days after the last dose of navitoclax. Events where the onset date was the same as the navitoclax start date were assumed to be treatment-emergent, unless the navitoclax start time and the AE start time were collected and the AE start time was prior to the navitoclax start time. If an incomplete onset date was collected for an AE, the AE was assumed to be treatment-emergent unless there was evidence that confirms that the AE was not treatment-emergent (e.g., the AE end date was prior to the date of the first dose of navitoclax).

Adverse event data was summarized and presented using primary MedDRA system organ classes (SOCs) and preferred terms (PTs) according to the MedDRA 22.0 coding dictionary.

The number and percentage of subjects experiencing treatment-emergent adverse events was summarized by phase 1 or 2, day cycle (14/21 or 21/21), navitoclax dose and for the whole portion of the study for the following adverse event summaries:

- Overview of treatment emergent adverse events
- Any treatment-emergent adverse event by System Organ Class and Preferred Term.
- Subject number associated with treatment-emergent adverse event.
- Treatment-emergent adverse events by System Organ Class, Preferred Term, and maximum NCI toxicity grade (CTCAE V3.0).

- Treatment-emergent adverse events broken down by maximum relationship to study drug.
- Any treatment-emergent NCI toxicity (CTCAE V3.0) grade 3 or 4 adverse events.
- Any treatment-emergent NCI toxicity (CTCAE V3.0) grade ≥ 3 adverse events.
- Treatment-emergent adverse events broken down by possibly or probably drug-related NCI toxicity grade ≥ 3 adverse events
- Treatment-emergent adverse events broken down by possibly or probably drug-related NCI toxicity grade 3 or 4 adverse events
- Any treatment-emergent adverse event with possibly or probably drug-related.
- For treatment-emergent serious adverse events, analyses similar to TEAE were provided.
- Any treatment-emergent adverse event leading to discontinuation of each drug.
- Any treatment-emergent adverse event leading to each drug interruption.
- Any treatment-emergent adverse event leading to each drug reduction.
- Any treatment-emergent adverse event leading to each drug delay.
- Any treatment-emergent adverse event leading to death.

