- Subject deaths occurring ≤ 30 days after last dose of study drug.
- Subject deaths occurring > 30 days after last dose of study drug.
- Any treatment-emergent DLT adverse events by primary MedDRA system organ class and preferred term.

Selected Adverse Events

Analysis of adverse events of safety areas of interest were conducted through the summary of MedDRA preferred terms identified using standard MedDRA queries (SMQs) and custom searches. Like TEAEs analyses, overview of selected AEs, and selected AEs by primary MedDRA system organ class and preferred term were provided. The search criteria for each of the safety areas of interest were described below.

Identified Risks

Thrombocytopenia - PTs: 10043554 Thrombocytopenia; 10035528 Platelet count decreased

Neutropenia - PTs: 10001507 Agranulocytosis; 10016288 Febrile neutropenia; 10029354 Neutropenia; 10059482 Neutropenic infection; 10049151 Neutropenic sepsis; 10029366 Neutrophil count decreased

Lymphopenia - PTs: 10025327 Lymphopenia; 10025256 Lymphocyte count decreased

Potential Risks

Hemorrhagic Events - SMQ 20000038 Hemorrhages (Narrow)

Opportunistic Infections - SMQ 20000235 Opportunistic Infections (Broad)

Tumor Lysis Syndrome - SMQ 20000219 Tumor Lysis Syndrome (Narrow)

Hepatotoxicity - SMQ 20000006 Drug Related Hepatic Disorders – Comprehensive (Broad); SMQ 20000007 Drug Related Hepatic Disorders – Severe Events Only (Narrow)

Increased Pancreatic Enzymes - SMQ 20000022 Acute Pancreatitis (Narrow)

Cardiovascular Events - SMQs: 20000004 Cardiac Failure (Narrow); 20000130 Pulmonary Hypertension (Narrow)

Venous Thromboembolic Events - SMQ 20000084 Embolic and Thrombotic Events, Venous (Narrow)

Cerebellar Hypoplasia - PT 10008033 Cerebellar Hypoplasia

Decreased Spermatogenesis - SMQ 20000210 Fertility Disorders (Narrow; males only)

Skin Cancer or Second Malignancies - SMQs: 20000173 Skin Neoplasms, Malignant and Unspecified (Broad); 20000090 Malignancies (Broad)

Allergic Reactions - SMQ 20000021 Anaphylactic Reaction (Broad)

Drug Interactions - HLT 10022528 Interactions

Analysis of Laboratory and Vital Signs Data

The value for baseline used in laboratory and vital sign analyses is defined in the Definition of Baseline section. All laboratory and vital signs were summarized by dose and the study portion as a whole.

Analysis of Mean Changes from Baseline in Clinical Laboratory Data

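### The SAP's search for second malignancies states no exclusion of CLL, so treatment-emergent events coded to the study disease can be counted as second cancers

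*SAP*

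**What the plan says.** The SAP's Selected Adverse Events section introduces its list of safety areas with "The search criteria for each of the safety areas of interest were described below". The lines that follow are therefore the operative definitions. The line for new cancers is "Skin Cancer or Second Malignancies - SMQs: 20000173 Skin Neoplasms, Malignant and Unspecified (Broad); 20000090 Malignancies (Broad". Neither that line nor any other part of the SAP removes CLL, its progression or its transformation, or asks whether a tumor is a new primary.

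Elsewhere in the same list the SAP does write in a restriction when it wants one: "Decreased Spermatogenesis - SMQ 20000210 Fertility Disorders (Narrow; males only".

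On scope and display, the SAP states "All analyses involving AEs were treatment-emergent adverse events (TEAE) only, unless otherwise specified". For the selected areas, "overview of selected AEs, and selected AEs by primary MedDRA system organ class and preferred term were provided".

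On what counts as an adverse event, Protocol Section 6.1.1 says "Any worsening of a pre-existing condition or illness is considered an adverse event". In the response criteria (Protocol Sections 5.3.3.1.1 and 5.3.3.1.2), "Transformation to a more aggressive histology", with Richter's syndrome and PLL as the examples, is one of the conditions that define progressive disease.

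**The concern.** A second-malignancy category should show whether new cancers appear after treatment. That reading requires the disease under treatment to be kept out. Here the searched concept is malignancy in general, and every subject already has one: Protocol Section 5.1 itself places CLL among the lymphoid malignancies when it describes the companion study. If CLL worsening is entered as an adverse event and coded to a malignancy term, a failure of the drug against CLL is added to a count that readers will take as a new-cancer risk.

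What is at stake is the interpretation of one line in the safety overview. No efficacy endpoint, dose decision, test or sample size depends on it.

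**Working it through.** The SAP gives no figure for this category, so there is nothing to reproduce. The check is a reading of the rule, followed by simple arithmetic on what one affected subject would do.

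**Can a study-disease event reach this category under the written rules?**

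1. *Is it an adverse event?* Protocol Section 6.1.1 includes worsening of existing illness. The section lists exemptions (certain laboratory and vital-sign changes, pre-planned surgery, hospital admission for tumor lysis prophylaxis as an SAE). None covers CLL progression. Section 6.5 was not in the text available for review, so an exemption there cannot be ruled out.
2. *Is it treatment-emergent?* The SAP window runs from the first dose to 30 days after the last. Protocol Section 5.4.1 makes progression a reason for discontinuation, so progression found on treatment falls inside the window.
3. *Does the search pick it up?* The query is the general malignancy query at broad scope. The documents do not list its preferred terms. That CLL terms belong to it is an inference from its name and scope.
4. *Does anything remove it afterwards?* Nothing in the SAP does.

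Steps 2 and 4 rest on the text. Step 1 rests on the text, subject to Section 6.5. Step 3 is an assumption.

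**Direction.** Let A be the subjects with a true new primary and B the subjects whose only hit is a study-disease term. The category counts A plus B. B cannot be negative, so the count can only be raised. A subject with both kinds of event adds nothing.

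**Size.** Inputs: 29 treated subjects in Phase 1 and 31 in Phase 2 (SAP, Data Sets Analyzed). With k subjects in B, the overstatement in percentage points is 100 × k / N. The documents do not give k. The range 0 to 3 is an assumption for illustration.

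| k (assumed) | Phase 1, N = 29 | Phase 2, N = 31 |
|---|---|---|
| 0 | 0 | 0 |
| 1 | 1/29 = 3.4 | 1/31 = 3.2 |
| 2 | 2/29 = 6.9 | 2/31 = 6.5 |
| 3 | 3/29 = 10.3 | 3/31 = 9.7 |

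**The case against.** The strongest reply is that an unstated rule is not a demonstrated bias. A reader might infer from the search line that CLL worsening was in fact reported as second cancer and that the published rate is too high. The documents do not support that. It would require progression to have been recorded as an adverse event, coded to a malignancy term, and that term to sit in one of the two queries. None of these is shown for any subject.

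Progression also has its own route into the data: a scheduled clinical progression assessment in Phase 2a (Table 3), a progression date on the Extension Study case report form, a discontinuation reason in Section 5.4.1, and the PFS and TTP endpoints in Section 8.1.3. Sites may never have entered it as an adverse event. Section 6.5 is a natural place for such an instruction. This objection stands, and it is why the point is worded as what the rule permits.

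A second reply is that the selected events are also tabulated by preferred term, where a CLL or Richter's term would appear by name. That largely stands too. It does not repair the overview, where the category count stands alone. Nor does a term-level table give the number of distinct subjects with a new primary.

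A third reply concerns transformation. The protocol classes it as progressive disease for response assessment, but does not say how safety tables should treat it. Dropping Richter's syndrome and PLL from the table outright would settle a medical question that the documents leave open. This stands, and the fix reflects it.

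**Conclusion.** The concern holds as a gap in the definition. The search states no exclusion of the study disease, and the readable protocol makes worsening of existing illness an adverse event. Treatment-emergent events coded to CLL or its progression can therefore be counted as second malignancies. Any effect is upward only, at the per-subject sizes shown above, and falls mainly on the overview or category count.

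This rests on two assumptions: that Section 6.5 contains no exemption for disease progression, and that CLL terms fall within the broad malignancy query. The conclusion does not extend to saying that the reported incidence is biased, because the number of affected subjects is unknown and may be zero. Severity is minor.

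**What to change.** Define the category as SMQ 20000173 and SMQ 20000090, excluding preferred terms for CLL and for CLL progression. Show the excluded events in a separate disease-related row. Show transformation events (Richter's syndrome, PLL) on their own line, so that they are neither merged with new primaries nor lost.

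The cost is a sentence of SAP text, a short term list and a brief medical review of that list. No data collection changes. The SAP is written in the past tense with final subject counts, so the table may already exist. In that case the same split can be added as a clearly labelled supplementary display. If Section 6.5 does exempt progression from adverse event reporting, a cross-reference to it would answer the point for progression, and the separate line for transformation would still help the reader.

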The safety of ABT-263 has been evaluated in single- and repeat-dose (up to 6 and 9 months in duration in rats and dogs, respectively), reproductive (male and female fertility and embryo fetal development), safety pharmacology (cardiovascular, neurofunctional, and pulmonary), genetic (Ames, in vitro cytogenetics, and in vivo micronucleus), and special studies (guinea pig sensitization; lymphocyte immunophenotyping; and single-dose oral toxicity in male rats). The primary effects of ABT-263 were on the hematopoietic system (platelets and lymphocytes) and the male reproductive system (germ cell depletion), and are believed to be based on inhibition of one or more members of the Bcl-2 family of antiapoptotic proteins. Other findings included ovarian atrophy (rats only), and generally minimal and reversible liver changes (single-cell hepatocellular necrosis, increased mitotic index, and hypertrophy/hyperplasia and pigmentation of Kupffer cells) and single-cell necrosis in various tissues. ABT-263 was neither genotoxic, nor did it affect male or female fertility in rats or embryo-fetal development in rats and rabbits. ABT-263-related effects were observed on brain, testes, and circulating platelets in juvenile rats. Effects on the brain (cerebellar hypoplasia), which were not observed in adult rats, were the likely result of incomplete maturation of the blood-brain-barrier at the time dosing was initiated in the rat pups (post natal Day 7).

ABT-263 caused increases in pulmonary and peripheral vascular resistance and decreases in cardiac output in the dog following acute or multiple daily dosing. Despite the increases in vascular resistance, there were no increases in blood pressure. On Day 28 of the oral dosing study, these cardiovascular effects were associated with a mean C_{\max} value of 16.6 $\mu\text{g/mL}$, whereas no statistically significant hemodynamic changes were associated with a mean C_{\max} of 11.4 $\mu\text{g/mL}$.¹³ Similar systemic exposures induced these effects in the acute cardiovascular study.

Chronic Lymphocytic Leukemia (CLL)

Chronic lymphocytic leukemia (CLL) is a monoclonal disorder characterized by a progressive accumulation of functionally incompetent lymphocytes. It is the most

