- Days 1, 2, 3, 5, 8, 14 and 16
- Platelet counts performed in Cycle 1 can be obtained within 24 hours prior to the visit, except on Days 1 and 14 when platelet counts are required at all of the pharmacokinetic sampling time points as indicated in [Table 4](#).
- As needed

Subsequent Cycles:

- Weekly

- As needed
- If the investigator and the AbbVie Medical Monitor jointly agree that platelet counts through Cycle 4 have been stable, then the frequency of platelet counts in Cycle 5 and beyond may be decreased to Day 1 of each cycle and as needed.

Final Visit and Safety Follow-up Visit

For the Extension Study, platelet count assessments will be performed at Day 1, every 4 cycles (e.g., Cycle 4 Day 1, Cycle 8 Day 1, etc.), Final Visit and at the Safety Follow-up Visit.

Phase 2a:

Screening

During the lead-in period, the following platelet counts will also be obtained:

- Lead-in Days 1, 2, 3, 5 and 7
- Daily if lead-in period extends beyond Day 7 (i.e., Lead-in Days 8-14)

Cycle 1:

- Days 1, 2, 3, 5, 8 and 15
- As needed

Subsequent Cycles:

- Weekly
- As needed
- If the investigator and the AbbVie Medical Monitor jointly agree that platelet counts through Cycle 4 have been stable, then the frequency of platelet counts in Cycle 5 and beyond may be decreased to Day 1 of each cycle and as needed.

Final Visit and Safety Follow-up Visit

For the Extension Study, platelet count assessments will be performed at Day 1, every 4 cycles (e.g., Cycle 4 Day 1, Cycle 8 Day 1, etc.), Final Visit and at the Safety Follow-up Visit.

Lymphocyte Enumeration

Lymphocyte enumeration to identify B and T cell lymphocyte subpopulations will be performed at Screening, Day 14 of Cycle 1 (14/21 day dosing schedule), Day 15 of Cycle 1 (21/21 day dosing schedule), end of Cycle 4, at the end of every 3rd cycle thereafter, and at the Final Visit for each subject. The lymphocyte enumeration results from Screening will serve as the baseline for clinical assessment. For the Extension Study, lymphocyte enumeration will be performed if deemed necessary by the investigator and at the Final Visit.

All lymphocyte enumeration results obtained in the Phase 1 portion of the study will be either entered immediately on the eCRF or faxed to the Oncology Safety Management Team within 24 hours of report availability via the contact information provided in Section 6.5.

ECOG Performance Status

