6.7.3 Management of Lymphopenia

There is a potential for clinically significant lymphopenia in this study. If clinically indicated, anti-infective prophylaxis should be implemented at the investigator's discretion, including appropriate prophylaxis for viral, fungal, bacterial or *Pneumocystis carinii* pneumonia (PCP) infections. Potential for drug-drug interactions should be considered. See [Appendix E](#) for a description of excluded and cautionary medications.

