Changes from baseline were analyzed for each scheduled post-baseline visit and for the final visit for lymphocyte enumeration, urinalysis, blood chemistry and hematology parameters, as well as vital sign parameters.

Laboratory tests to be summarized are included in Table 1.

Table 1. Clinical Laboratory Tests

Hematology	Chemistry	Urinalysis
Hematocrit	Blood Urea Nitrogen (BUN)	Urine PH
Hemoglobin	Creatinine	Urine specific gravity
Red Blood Cell (RBC) count	Total bilirubin	Lymphocyte Enumeration
White Blood Cell (WBC) count	Serum glutamic-pyruvic transaminase (SGPT/ALT)	B-Lymphocytes total
Neutrophils	Serum glutamic-oxaloacetic transaminase (SGOT/AST)	Natural killer cells total
Bands	Alkaline phosphatase	T-Helper cells total
Lymphocytes	Sodium	T-Lymphocytes total
Monocytes	Potassium	T-Suppressor cells total
Basophils	Calcium	
Eosinophils	Inorganic phosphate	
Platelet count	Uric acid	
Reticulocyte count	Cholesterol	
Prothrombin time (PT)	Total protein	
Activated partial thromboplastin time (aPTT)	Glucose	
Mean corpuscular volume (MCV)	Triglycerides	
MPV	Albumin	
MCH	Lactate dehydrogenase (LDH)	
MCHC	Magnesium	
	Chloride	
	Bicarbonate	
	Lipase	

Mean changes from baseline at each scheduled post-baseline visit and Final Visit was summarized with the baseline mean, visit mean, change from baseline mean, standard deviation, and minimum/maximum values.

Analyses of Shift from Baseline in Clinical Laboratory Data

For shifts relative to National Cancer Institute Common Toxicity Criteria for Adverse Events (NCI CTCAE), baseline and post-baseline laboratory observations were categorized as grade 0, grade 1, grade 2, grade 3, or grade 4 according to NCI CTCAE grade version 3.0.

The baseline and final grades were defined respectively as the grade of the last measurement collected prior to the first dose of navitoclax, and as the last post-baseline

measurement collected no more than 30 days after the last dose of navitoclax. The maximum NCI toxicity grade value was the value with highest NCI toxicity grade collected after the first dose of navitoclax and within 30 days following the last dose of navitoclax. In cases where multiple values are collected on the same day, the maximum grade value was selected as the value for that day.

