For each variable, shift tables were generated that cross tabulate the number of subjects with baseline values of grade 0, grade 1, grade 2, grade 3, or grade 4 versus final observations of grade 0, grade 1, grade 2, grade 3, or grade 4.

Additionally, for each variable, the number and percentage of subjects that have a baseline observation that was categorized as a grade 0, grade 1, or grade 2 and that also have a grade 3 or 4 final observation was presented. In addition to final observation, a similar set of summaries were produced for the maximum post-baseline laboratory observations.

For urinalysis, cross tabulated the number of subjects with baseline and maximum dipstick results. Similar cross tabulations were provided for baseline and final dipstick results.

Detailed listings of data for subjects experiencing NCI CTCAE grade 3 to 4 blood chemistry and hematology values were provided. Listings were also provided for urinalysis values with dipstick results of 2+ or higher. All measurements collected, regardless of the number of days after the last dose of navitoclax, were included in these listings.

The NCI CTCAE grade 3 criteria are given in Table 2 and Table 3 below.

Table 2. Criteria for Potentially Clinically Significant Laboratory Values – Chemistry Variables

Chemistry Variables	Units	Definition of Potentially Clinically Significant Current (Version 3) Grade 3	
		Low	High
Total bilirubin	mcmol/L		> 3.0 × ULN
Albumin	g/L	< 20	
Aspartate amino transaminase (AST/SGOT)	U/L		> 5.0 × ULN
Alanine amino transferase (ALT/SGPT)	U/L		> 5.0 × ULN
Alkaline phosphatase	U/L		> 5.0 × ULN
Creatinine	mcmol/L		> 3.0 × ULN
Sodium	mmol/L	< 130	> 155
Potassium	mmol/L	< 3.0	> 6.0
Total calcium	mmol/L	< 1.75	> 3.1
Glucose	mmol/L	< 2.2	> 13.9
Inorganic Phosphate	mmol/L	< 0.6	
Bicarbonate	mmol/L	< 11	
Cholesterol	mmol/L		> 10.34
Triglycerides	mmol/L		> 5.0 × ULN
Magnesium	mmol/L	< 0.4	> 1.23

Table 3. Criteria for Potentially Clinically Significant Laboratory Values – Hematology Variables

Hematology Variables	Units	Definition of Potentially Clinically Significant Current (Version 3) Grade 3	
		Low	High
Hemoglobin	g/L	< 80	
White blood cell count	10 ⁹ /L	< 2	
Neutrophils	10 ⁹ /L	< 1	
Lymphocytes	10 ⁹ /L	< 0.5	
Platelets	10 ⁹ /L	< 50	

Assessment of Mean Changes from Baseline in Vital Signs Variables

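### Laboratory lymphopenia is graded, shifted and listed only on total lymphocytes, so circulating CLL cells can hide loss of normal lymphocytes, and clearing them can look like new lymphopenia

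*SAP*

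**What the plan says.** **Grading and shifts.** Under Analyses of Shift from Baseline in Clinical Laboratory Data, the SAP has laboratory observations "categorized as grade 0, grade 1, grade 2, grade 3, or grade 4 according to NCI CTCAE grade version 3.0". It cross-tabulates baseline against final and maximum grade. It also counts subjects who move from grade 0-2 at baseline to grade 3 or 4.

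**Limit.** The lymphocyte row of SAP Table 3 reads "Lymphocytes 10 ⁹ /L < 0.5". It sits among the hematology variables. No row covers a lymphocyte subset.

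**Listings.** "Detailed listings of data for subjects experiencing NCI CTCAE grade 3 to 4 blood chemistry and hematology values were provided". Lymphocyte enumeration has its own heading in SAP Table 1 and is not named here.

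**Subsets.** Protocol 5.3.1.1 says "Lymphocyte enumeration to identify B and T cell lymphocyte subpopulations will be performed at Screening", and at later visits. SAP Table 1 lists B, NK, T-helper and T-suppressor totals and "T-Lymphocytes total". For these the SAP says "Changes from baseline were analyzed for each scheduled post-baseline visit and for the final visit for lymphocyte enumeration". The summary gives baseline mean, visit mean, mean change, standard deviation, minimum and maximum.

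**The risk.** The SAP names lymphopenia as an identified risk under Selected Adverse Events. Protocol 6.7.3 says "There is a potential for clinically significant lymphopenia in this study". The HIV exclusion criteria link lymphopenia to opportunistic infection.

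**The concern.** Protocol 3.0 says that CLL "is a monoclonal disorder characterized by a progressive accumulation of functionally incompetent lymphocytes". The protocol also uses the blood lymphocyte count as a measure of disease: a fall of at least 50% counts towards PR, and a rise of at least 50% towards PD (5.3.3.1.1 and 5.3.3.1.2). The laboratory outputs for lymphopenia use that same count. One number then carries two quantities, tumor burden and normal lymphocytes, which can move separately under treatment.

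The adverse event route does not close the gap. Under protocol 6.1.1 a laboratory abnormality becomes an adverse event only if it leads to discontinuation or intervention, meets protocol criteria, or is judged to be one by the investigator. The graded laboratory tables are therefore the main objective, subject-level evidence on this risk. At stake is whether a reader can learn from them how many subjects lost normal lymphocytes on navitoclax.

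**Working it through.** The 0.5 limit is a definition, so there is no planned figure to reproduce. The check asks what the limit can and cannot detect.

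**Inputs from the documents**
- Limit: total lymphocytes < 0.5 × 10⁹/L (SAP Table 3).
- Shift rule: baseline grade 0-2 to grade 3-4, at final or maximum (SAP).
- PR lymphocyte criterion: fall of at least 50% (protocol 5.3.3.1.1).
- 1996 CR lymphocyte level: < 4 × 10⁹/L (protocol Table 10), which is 4 / 0.5 = 8 times the limit.

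**Assumptions** (not in the documents)
- Starting clone: 5 to 100 × 10⁹/L.
- Remaining normal lymphocytes: 0 or 0.2 × 10⁹/L.
- The laboratory's lower limit for total lymphocytes lies below 5 × 10⁹/L.

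**Step 1: insensitivity.** Write total = N + C, with N normal and C clonal lymphocytes. The total is below 0.5 only if the clone has fallen by more than 1 − (0.5 − N)/C.

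| Starting clone (× 10⁹/L) | N = 0 | N = 0.2 |
|---|---|---|
| 5 | 1 − 0.5/5 = 90% | 1 − 0.3/5 = 94% |
| 10 | 95% | 97% |
| 20 | 97.5% | 98.5% |
| 50 | 99% | 99.4% |
| 100 | 99.5% | 99.7% |

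With every normal lymphocyte lost and 90% of the clone cleared, totals of 20, 50 and 100 become 2, 5 and 10. None is flagged.

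**Step 2: example of a missed case.** The total falls from 20 to 5 with complete T-cell loss. The fall is 1 − 5/20 = 75%, which meets the PR lymphocyte criterion. The count of 5 is 5 / 0.5 = 10 times the limit, so the subject is graded 0.

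**Step 3: can a single value be flagged wrongly?** No. N cannot exceed the total, so a total below 0.5 forces N below 0.5. A grid with N from 0 to 3 and C from 0 to 100 gave no flagged case with N at or above 0.5.

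**Step 4: can a shift mislead?** Yes. Keep N at 0.4 throughout and let the clone fall from 20 to 0. The total goes from 20.4 to 0.4. The SAP counts this as a move from grade 0 to grade 3 or 4, although normal lymphocytes were low at baseline and did not change.

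**Step 5: what the subset summaries add.** They show the average change at a visit and the extremes. They do not give the number of subjects who became depleted, identify them, or show each subject's worst value.

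**The case against.** The strongest reply is that the plan does look at normal lymphocytes. Subset totals are analyzed at each scheduled visit, by dose, with minimum and maximum, and protocol 8.1.4 has enumeration explored for trends with dose and time. In Phase 1, enumeration results reach the sponsor's safety team within 24 hours. Opportunistic infections are searched directly with a broad MedDRA query. All of this stands, and it means the loss is not hidden throughout the plan. It still gives no subject-level subset count, shift or listing. The shift section does speak of each variable, but the SAP states no criterion by which a subset would be graded.

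It is also true that no decision rests on this row. Protocol 6.7.1 exempts grade 3-4 lymphopenia from the DLT definition, and the tables are descriptive, in 29 Phase 1 and 31 Phase 2 subjects. That limits the consequence to what can be concluded about an identified risk.

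Finally, the size is unknown. Eligibility sets no minimum lymphocyte count, and subjects with few circulating CLL cells would be graded about correctly. This stands in full.

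A reader might go further and infer that the flag marks deep response rather than lymphopenia. Step 3 rules that out for a single value: anyone below 0.5 does have low normal lymphocytes. Only the shift, read as on-treatment loss, can mislead in that direction.

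**Conclusion.** The point holds in limited form and merits a change. The graded, shifted and listed laboratory outputs for lymphopenia rest on a count that includes CLL cells. Two errors follow in subjects with a sizeable circulating clone. Loss of normal lymphocytes can be graded 0. In the shift tables, clearance of the clone can also register as new grade 3-4 lymphopenia when normal lymphocytes were already below 0.5 × 10⁹/L and stayed there.

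The percentages in the working depend on assumed starting counts. The number of subjects affected cannot be computed. A reader might infer that most lymphocytes are tumor cells in every subject, but the protocol's description of CLL is qualitative and gives no tumor fraction. Nothing here bears on the MTD, the DLT definition or an efficacy endpoint.

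**What to change.** From the enumeration data already collected:

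1. Add a low/normal shift table for T-lymphocyte, T-helper and NK totals, classed against the laboratory's lower limit at baseline, worst and final value, with subject counts.
2. Add a subject listing of low subset values.
3. Label both as descriptive and not as a CTCAE grade. Do not carry the 0.5 limit over to T plus NK: the SAP gives it for total lymphocytes, and the sum leaves out normal B cells.
4. Footnote the total-lymphocyte row, in Table 3 and in the shift and listing outputs, as including CLL cells.

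The cost is a few rows and one listing, with no new sampling and no change to conduct. The drawback is sparse data. Enumeration takes place at Screening, Cycle 1 Day 14 or 15, the end of Cycle 4, every third cycle after that and the Final Visit. In the Extension it takes place only at the Final Visit or as needed. The worst value therefore rests on few time points, and the table should say so.
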